  - Time to intensification from BL of antihypertensive therapy
  - Proportion of subjects with increase in BP, defined as an increase from BL of  $\geq 20$  mm Hg sBP and sBP > 170 mmHg or an increase from BL of  $\geq 15$  mm Hg dBP and dBP > 100 mmHg
  - Proportion of subjects with a treatment-emergent AE of hypertension
  - Proportion of subjects with intensification from BL of antihypertensive therapy
- Vascular Access Thrombosis (HD subjects):
  - Time to a treatment-emergent AE of vascular access thrombosis
  - Proportion of subjects with a treatment-emergent AE of vascular access thrombosis
- HRQoL and EQ-5D-5L Benefits of Anemia Therapy:

Change from BL to the average of Weeks 12 to 28 and 28 to 52 of treatment for those listed below.

- VT Subscale of SF-36: In subjects with BL VT Subscore below 50
- Physical Component Scores of SF-36:
  - In subjects with BL *physical component scores* below 40
  - In all subjects
- Anemia Subscale (“Additional Concerns”) of Functional Assessment of Cancer Therapy-Anemia (FACT-An) Scores:
  - In subjects with BL subscale scores below 55 (generally associated with fatigue).
  - In all subjects
- Total FACT-An Scores:
  - In subjects with BL FACT-An scores below 135
  - In all subjects
- *EQ-5D-5L Scores*: In all subjects
- Hepcidin, Iron Indices, and HbA1c:
  - Change from BL in serum hepcidin at each of the selected time points
  - Change from BL in serum ferritin at each of the selected time points, total and subgrouped by BL values of  $\leq 400$  ng/mL, and  $> 400$  ng/mL.
  - Change from BL in TSAT at each of the selected time points, total and subgrouped by BL values of  $\leq 40\%$ , and  $> 40\%$ .
  - Change in HbA1c level at each of the selected time points in all subjects, in subjects with history of diabetes

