#### **7.9.1 36-Item Short Form Health Survey**

The 36-Item Short Form Health Survey (SF-36) is a quality of life (HRQoL) instrument designed to assess generic health concepts relevant across age, disease, and treatment groups. It is aimed at both adults and adolescents ages 18 years and older. The SF-36 consists of 8 domains of health status: physical functioning (PF) (10 items), role physical (4 items), bodily pain (2 items), general health (5 items), vitality (VT) (4 items), social functioning (2 items), role emotional (3 items) and mental health (5 items). Two component scores, the Physical Component Scores and

the Mental Component Summary can also be calculated. For both the SF-36 domain scores and summary scores, higher scores indicate better health status.

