- **Health Related Quality of Life (HRQoL) and EQ-5D-5L Benefits of Anemia Therapy:**

Change from baseline averaged over Weeks 12 to 28, and 28 to 52 of treatment for parameters listed below.

 - Vitality Sub-score of SF-36 (Appendix 3):
 - In FAS subjects with baseline Vitality Sub-score below 50.
 - In all FAS subjects.

- Physical Functioning Sub-score of SF-36:
 - In FAS subjects with baseline Physical Functioning Sub-score below 40.
 - In all FAS subjects.
- Anemia Subscale (“Additional Concerns”) of Functional Assessment of Cancer Therapy-Anemia (FACT-An) Scores (Appendix 4):
 - In FAS subjects with baseline subscale scores below 55 (generally associated with fatigue).
 - In all FAS subjects.
- Total FACT-An Scores:
 - In FAS subjects with baseline FACT-An scores below 135
 - In all FAS subjects.
- EQ-5D-5L Scores and other QoL Measures/Other Component scores of SF-36: In all FAS subjects.
- **Hepcidin, Iron Indices, and HbA1c:**
 - Change from baseline in serum hepcidin at each of the selected time points
 - Change from baseline in serum ferritin at each of the selected time points, total and sub-grouped by baseline values of <400 ng/mL, and \geq 400 ng/mL.
 - Change from baseline in TSAT at each of the selected time points, total and sub-grouped by baseline values of <40%, and \geq 40%.
 - Change in HbA1c level at each of the selected time points, in all subjects, in subjects without history of diabetes and in subjects with history of diabetes.

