11.3.7 Health Related Quality of Life (HRQoL) and EQ-5D-5L Benefits of Anemia Therapy

The Medical Outcomes Study 36-Item Short-Form Health Survey (SF-36) is a multi-purpose, short-form health survey with 36 questions (Appendix 3). It yields an 8-scale profile of functional health and well-being scores as well as psychometrically-based physical and mental health summary measures. It is a generic measure, as opposed to one that targets a specific age, disease, or treatment group. Accordingly, the SF-36 has proven useful in surveys of general and specific populations, comparing the relative burden of diseases, and in differentiating the health benefits produced by a wide range of different treatments.

The SF-36 contains 36 items that measure eight dimensions: (1) physical functioning (PF); (2) role limitations due to physical health problems (RP); (3) bodily pain (BP); (4) social functioning (SF); (5) general health perceptions (GH); (6) role limitations due to emotional problems (RE); (7) vitality, energy or fatigue (VT); and (8) mental health (MH).

Item scores for each dimension are coded, summed, and transformed to a scale from 0 to 100, with higher scores indicating better self-perceived health (Table 7). The transformed items are then averaged to give the subscales. The subscales are averaged to give the composite scores. The composite scores are averaged to give the overall score. The reliability and validity of the SF-36 is well documented in a variety of different subject groups, including subjects with vascular diseases.

[figure not shown]
Table 7. Transformation of SF-36 items to a Scale from 0 to 100

Question	Self-perceived health
----------	-----------------------

	0 (Poor)	100 (Better)
1, 2, 6, 8, 9a, 9d, 9e, 9h, 11b, 11d	5	1
3a to 3j	1	3
4a to 4d, 5a to 5c, 9b, 9c, 9f, 9g, 9i, 10, 11a, 11c	1	5
7	6	1
Programming note: Once transformed – the items should each span the range 0 to 100.		

For each of the 8 dimensions, if less than 50% of the items which constitute that dimension are missing, the dimension score will be calculated by the mean of the available non-missing items. The physical health composite summary and mental health composite summary will only be calculated if a score has been calculated for all 4 dimensions that constitute the composite summary.

Figure 3. SF-36 Model

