Change from baseline in SF-36 PF sub-score to the average PF sub-score of weeks 12 to 28 will be analyzed using MMRM model with baseline PF subscore as a covariate, treatment group, visit, the interaction of treatment and visit, and stratification factors as fixed effects. The same strategy as that used in MMRM for Hb will be used to choose variance covariance structure. Data up to visit of Week 52 will be included in the analyses. The estimates for the difference of change from baseline in SF-36 PF for Week 12 to 28 between the two treatment groups will be generated from an estimate statement.

- Vitality Sub-score of SF-36: In subjects with baseline vitality sub-score below 50.
- Physical Functioning Sub-scores of SF-36:
 - In FAS subjects with baseline physical Functioning scores below 40.
 - In all FAS subjects.
- Anemia Subscale (“Additional Concerns”) of Functional Assessment of Cancer Therapy-Anemia (FACT-An) Scores:
 - In FAS subjects with baseline subscale scores below 55 (generally associated with fatigue).
 - In all FAS subjects.
- Total FACT-An Scores:
 - In FAS subjects with baseline FACT-An scores below 135
 - In all FAS subjects.
- EQ-5D-5L Scores: In all FAS subjects.

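### The SAP moves the protocol's baseline cut-off of 40 from the SF-36 Physical Component Score to the Physical Functioning subscale, so the low-baseline component-score analysis is dropped

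*SAP*

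**What the plan says.** The quality-of-life list in protocol 3.2.3 contains "Physical Component Scores of SF-36" with two populations: "In subjects with BL *physical component scores* below 40", and all subjects. Change is from baseline to the averages of Weeks 12 to 28 and Weeks 28 to 52.

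SAP 4.3 keeps the list and the averaging periods. In the component score's place it has "Physical Functioning Sub-score of SF-36", again with two populations: "In FAS subjects with baseline Physical Functioning Sub-score below 40", and all FAS subjects. The endpoint list in SAP 11.3.7 says the same: "In FAS subjects with baseline physical Functioning scores below 40".

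Both documents treat these as different scores. Protocol 7.9.1 describes PF as a ten-item domain, one of eight, and then introduces the summaries: "Two component scores, the Physical Component Scores and" its mental counterpart. SAP 11.3.7 lists PF among eight dimensions and says of the summaries: "The subscales are averaged to give the composite scores". It requires all four constituent dimensions before a composite is calculated.

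The only other place for component scores in the SAP's endpoint lists is a catch-all line in SAP 4.3, covering EQ-5D-5L, other quality-of-life measures and other SF-36 component scores, for all FAS subjects.

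**The concern.** A baseline cut-off has meaning only on the score for which it was set. Here the number 40 has been carried from a four-dimension summary to a single subscale, and no reason is given for using 40 on that subscale. Two things follow for a programmer who works from the SAP as written. An analysis that the protocol declares, the component score in subjects who start low on it, will not be produced. A subset that the protocol does not declare, PF below 40, will be reported where a reader of the protocol expects the other one.

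At stake is whether the reported low-baseline physical-health result is the one that was declared. The outcome is self-reported and the trial is open-label, so an unexplained change of score and subset is likely to prompt questions about selection even if it is only a drafting slip.

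**Working it through.** The plan gives no figure to reproduce here. The check is a comparison of texts, followed by arithmetic to see whether the two subsets can differ in practice.

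**Step 1. Cut-offs side by side (protocol 3.2.3 against SAP 4.3).**

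| Cut-off | Score in protocol | Score in SAP |
|---|---|---|
| 50 | SF-36 Vitality | SF-36 Vitality |
| 40 | SF-36 Physical Component Score | SF-36 Physical Functioning |
| 55 | FACT-An Anemia Subscale | FACT-An Anemia Subscale |
| 135 | Total FACT-An | Total FACT-An |

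Only the 40 has moved.

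**Step 2. Is the component score below 40 analysed anywhere else in the SAP?** No. The catch-all line in SAP 4.3 covers all FAS subjects only and does not name the physical score. The list in SAP 11.3.7 omits that line and ends with EQ-5D-5L. The text of 11.3.7 says only that other quality-of-life variables may also be analysed.

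**Step 3. Can the subsets differ?** Use the SAP's averaging, composite = (sum of the four dimension scores) / 4, each on 0 to 100. Assume PF is one of the four physical dimensions. SAP 11.3.7 gives the number four but does not name them in the text, and the SF-36 model figure is not reproduced in the copy available.

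- PF 35, others 50, 60, 45: (35 + 50 + 60 + 45) / 4 = 190 / 4 = 47.5. In the SAP subset, outside the protocol's.
- PF 45, others 30, 35, 40: (45 + 30 + 35 + 40) / 4 = 150 / 4 = 37.5. In the protocol's subset, outside the SAP's.

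**Step 4. By how much?** The documents give no distribution for these scores, so the inputs are assumptions: four normal dimension scores with common mean 40, 45 or 55, SD 22 or 28 and pairwise correlation 0.4, 0.6 or 0.8, then clipped to 0 to 100. Each of the 18 settings used 400,000 simulated subjects and compared PF below 40 with composite below 40. Selected rows:

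| Mean | SD | Correlation | In one subset only | Of PF < 40, outside composite < 40 | Of composite < 40, outside PF < 40 |
|---|---|---|---|---|---|
| 40 | 22 | 0.4 | 23.4% | 23.4% | 23.3% |
| 40 | 22 | 0.8 | 12.6% | 12.6% | 12.6% |
| 45 | 28 | 0.6 | 18.1% | 22.6% | 20.2% |
| 55 | 22 | 0.4 | 17.6% | 49.5% | 30.0% |
| 55 | 22 | 0.8 | 9.9% | 23.5% | 17.6% |

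Check on the fourth row: 24.7% have PF < 40 and 17.8% have composite < 40, so 0.247 × 0.495 + 0.178 × 0.300 = 0.122 + 0.053, or about 17.6% after rounding.

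Over all 18 settings, 9.9% to 23.4% of subjects fall in one subset only, and 12.6% to 49.5% of the PF-below-40 subset fall outside the component subset. Protocol 7.9.1 gives no scoring method for the component score, so these figures also rest on applying the SAP's averaging to the protocol's subset.

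**The case against.** Several stronger readings are tempting, and the other side is right to resist them.

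- **That an undeclared endpoint has replaced a declared one.** A reader might infer this from the endpoint lists alone. The documents do not support it for PF as a score: change in PF to the average of Weeks 12 to 28 is a secondary endpoint in protocol 3.2.2, with its own MMRM and a 2-point margin in protocol 9.4.3.2. The SAP takes PF and Vitality out of the secondary list and carries both as additional evaluations, which may explain how PF came to stand here. Only the PF-below-40 subset is new.
- **That the whole component-score endpoint is lost.** The all-subjects half arguably survives in the catch-all line of SAP 4.3, and SAP 11.3.7 still has rules for calculating the physical composite. But the score is not named there, and the 11.3.7 list omits the line.
- **That protocol 9.6 has been breached, or that data drove the change.** Protocol 9.6 asks for significant changes to be highlighted in the SAP. Whether a subgroup of an additional endpoint counts as significant is a judgement, and the SAP's front pages were not available, so a revision note there cannot be excluded. Nothing in the documents suggests that results influenced the choice.
- **That the percentages measure the trial.** They do not. The means, SDs and correlations are assumed, and so is PF's place in the physical composite. They show that the subsets can differ materially, not by how much they will.

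None of this restores the missing analysis: no SAP section covers the component score in subjects below 40.

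**Conclusion.** The point holds in a limited form. The SAP drops the protocol's analysis of the Physical Component Score in subjects with a baseline component score below 40. It adds a PF-below-40 subset that the protocol does not contain, and the SAP text available does not explain the change. The text comparison establishes this without any assumption.

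The size is conditional. If PF is one of the four physical dimensions, if the SAP's averaging applies, and with the assumed ranges of mean, SD and correlation, about 10% to 23% of subjects are in one subset only and about 13% to 50% of the PF-below-40 subset are outside the component subset.

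The consequence is minor. No SF-36 score is in the fixed sequence of SAP Table 6, so the primary result and type I error are unaffected. What suffers is fidelity to a declared additional analysis.

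**What to change.** In SAP 4.3 and 11.3.7, restore the Physical Component Score of the SF-36 as a named endpoint, in subjects with a baseline component score below 40 and in all subjects, analysed by the MMRM that 11.3.7 already sets out for the other quality-of-life scores. State that the 40 applies to the composite as the SAP scores it, since protocol 7.9.1 gives no scoring. If PF below 40 is kept, label it as an added analysis that is not in the protocol.

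The cost is SAP wording and one extra table. The SF-36 is already collected on Day 1 and at Weeks 12, 28 and 52.

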4.4 Safety Assessments

Study-specific Safety will be assessed by evaluating the following:

- treatment emergent adverse events (TEAEs), treatment emergent serious adverse events (TESAEs)
- Vital signs, electrocardiogram (ECG) findings, and clinical laboratory values

Safety interpretation will also be made based on analyses of adjudicated safety data pooled across multiple studies in the roxadustat Phase 3 program as described in PSAP. The members of an independent adjudication committee blinded to treatment assignment will adjudicate the following events in multiple phase 3 studies:

- Death from any cause, MI, stroke, heart failure requiring hospitalization, unstable angina requiring hospitalization, hypertensive emergency, deep venous thrombosis, pulmonary embolism, and vascular access thrombosis.

5 GENERAL STATISTICAL CONSIDERATIONS

5.1 Sample Size Determination

At least 600 subjects and up to 1200 subjects will be randomized via IXRS to receive roxadustat or epoetin alfa in a 1:1 ratio. Study drug will be administered in an open-label manner. Randomization will be stratified by the following four factors:

- Mean qualifying screening hemoglobin (≤ 10.5 vs. >10.5 g/dL)
- History of cardiovascular, cerebrovascular or thromboembolic diseases (Yes vs. No)
- Mean prescribed baseline epoetin alfa dose (or, equivalent epoetin dose for non-epoetin subjects) in 4 weeks prior to randomization (≤ 150 vs. >150 IU/kg/week)

Up to 600 subjects will be enrolled in this study in each treatment group. During the course of this study, which is being conducted in parallel with other Phase 3 studies, up to 1200 subjects may be enrolled for safety evaluation of roxadustat in comparison to epoetin alfa including pre-specified and adjudicated safety events of interest (i.e., all-cause death, MI, stroke, congestive heart failure requiring hospitalization, unstable angina requiring hospitalization, DVT, pulmonary embolism, vascular access thrombosis, and hypertensive emergency). The final number of patients to be enrolled will be based on the enrollment rate of other studies within the same indication, in order to optimize stopping these studies at comparable time frame.

With at least 600 subjects, the study will provide at least 99% power to demonstrate statistical non-inferiority of roxadustat versus ESA in the primary endpoint for US (FDA) submission (i.e., specifically, hemoglobin change from baseline to the average level during the evaluation period defined as Week 28 until Week 52).

The study will provide at least 99% power to demonstrate statistical non-inferiority of roxadustat versus ESA in the primary endpoint outside of the United States (i.e., specifically, hemoglobin change from baseline in the averaged hemoglobin over Weeks 28 to 36). This assumes a difference (roxadustat minus ESA) of -0.30 g/dL, a non-inferiority margin for this difference of 0.75 g/dL and a standard deviation of 1.25 g/dL. Appendix 7 has description on the justification that the non-inferiority margin of 0.75 was used.

5.2 Analysis Populations

5.2.1 Intent-to-Treat (ITT) Population

The ITT population consists of all randomized subjects. If treatment received differs from the randomized treatment, the randomized treatment group will be used.

5.2.2 Full Analysis Set (FAS)

The FAS population will consist of all randomized/enrolled subjects who received at least one dose of study drug and have at least one post-dose hemoglobin assessment. If treatment received differs from the randomized treatment, the randomized treatment group will be used.

5.2.3 Per Protocol Set (PPS)

The PPS population will consist of all subjects in the FAS population who received at least 8 weeks of treatment, have at least one valid post-dose hemoglobin assessment and are without Major protocol violations. If treatment received differs from the randomized treatment, the randomized treatment group will be used.

5.2.4 Safety Population (SAF)

The Safety Population will consist of all randomized/enrolled subjects who received at least one dose of study medication. If treatment received differs from the randomized treatment, the actual treatment group will be used.

5.2.5 Major Protocol Deviations

A subject who meets any of the major protocol deviation criteria in Table 3 will be excluded from the PPS. These will be identified while data are collected and a blinded review will occur before database lock.

Table 3. Criteria for Assessing Major protocol Deviations

Number	Major Protocol Deviation
1	Violation of key* inclusion or exclusion criteria which may affect the assessment of the efficacy of the study drug.
2	Administration of wrong randomization study drug for more than 4 weeks of wrong treatment before week 24; any duration from week 24 to week 52.
3	Study drug compliance < 75% (up to Week 52).
4	Administration of prohibited concomitant medication that may impact evaluation of study drug*.
5	Significant noncompliance with study procedures, that may impact evaluation of efficacy of the study, will be evaluated case by case*.

*Subject to Medical Monitor's decision

The number and percentage of Major protocol deviations will be categorized and summarized by treatment group as deemed appropriate.

5.3 Methodology and Conventions

Continuous variables will be presented by descriptive statistics: n, mean, standard deviation, median, minimum, and maximum. Categorical variables will be tabulated by frequency count and percentage. For efficacy endpoints, the standard error and 95% confidence intervals (CI) will be presented as part of the descriptive summaries.

Safety and efficacy data will be summarized and presented by treatment group and time point in summary tables.

Lab results obtained from the central laboratory will be used for all efficacy and safety analyses. Local laboratory values, if collected in the CRF's, will be listed only in data listing. Unless otherwise stated, all statistical tests will be two-sided hypothesis tests performed at the 5% level of significance for main effects and all confidence intervals will be two-sided 95% confidence intervals.

The secondary endpoints will be tested sequentially using the fixed sequence approach for multiplicity adjustments at an alpha level of 0.05. There will be no adjustments for multiple comparisons for other tests.

All analyses will be performed using SAS® Version 9.1.3 or higher.

5.4 Additional Data Handling Rules and Presentation Specifications

The following general guidelines will apply to all statistical analyses and data presentations:

- Baseline is defined as the last available value obtained prior to the first dose of study drug, unless otherwise specified in this SAP.
- Hemoglobin baseline is defined as the mean of the at least last three available central laboratory hemoglobin values obtained prior to the first dose of study medication (three

of the latest screening hemoglobin values plus the predose hemoglobin value collected on Day 1). In subjects with missing Day 1 hemoglobin value, the mean of three latest screening laboratory hemoglobin values will be considered as baseline hemoglobin value.

- Baselines for reticulocyte count, reticulocyte hemoglobin content (CHr), hepcidin, hs-CRP, serum iron parameters (transferrin, TIBC, ferritin, sTfR, and iron), blood pressures and heart rate are defined as the mean of central lab values obtained within 6 weeks prior to the first dose of study medication.
- Randomization stratification factors derived from actual data (not the ones from the randomization system) will be used in all applicable analysis models
 - The stratification factors to be included in the analyses, where appropriate, include the randomization stratification factors and incident dialysis within ≤ 4 months vs. > 4 months of starting dialysis when randomized.
- When the actual treatment received by a subject is different from the randomized treatment assigned, the subject will be analyzed per the randomized treatment for the efficacy parameters; while they will be analyzed per actual treatment that was taken for the safety parameters for US submission.
- Unscheduled visits within an allowable window will be grouped into the closest scheduled visits based on the visit window specified in Appendix 5. For subjects who have more than one measurement at a certain scheduled visit, the last measurements will be used, with the exception of CPK, WBC, liver function tests (i.e., ALT, AST, GGT, ALP, and total bilirubin), in which the maximum measurement will be used.
- By default, US conventional units will be used for laboratory value presentations. A set of lab summary tables in SI units will also be provided based on TLF index.
- Age is calculated as of date that the informed consent form was signed.

age = INTCK('YEAR', Birth date, date of Informed Consent, 'C') where INTCK is a SAS function.

- Duration of treatment or days in treatment is calculated as: last dose date of study medication – first dose date of study medication + 1
- Body weight, height and temperatures will converted using the following formula:
 - kg = lb/2.2
 - cm = 2.54 x in
 - C° = (5/9) x (F° – 32)
- The mean, standard deviation and median will be presented with adding one more decimal to raw data with rounding off. The minimum and maximum will be presented with the same number of decimals as in the raw data.
- All percentages will be rounded to one decimal place and lined up by the decimal place. The percentage will be suppressed when the count is zero.
- Any p-values will be rounded to four decimal places and will be presented as '<.0001' if they are less than 0.0001 after rounding.
- All tables and listings will have a header showing "FibroGen, Inc.", the protocol number, and Page x of y. Footer will indicate the program file path/name, run date and run time.
- For continuous variables that are recorded as "< X" or "> X", the value of "X" will be used in the calculation of summary statistics. The original values will be used for the listings.
- Decimal points will be presented as follows: N will be presented without decimal, minimum and maximum in same precision as in the database, mean and median in one

more decimal than minimum and maximum, and SD and SE in one more decimal than mean and median.

- Tables and figures will use derived analysis visit. Listings will use nominal visits, show the flag to indicate analysis visit to be used. Namely, both Nominal visit and analysis visit will be presented in the listing.
- Additional data handling conventions are detailed in Appendix 5.
- Analysis visits assigned for hemoglobin samples collection corresponding to the range of treatment days (window) during which an actual visit may have occurred are presented in Appendix 5. All scheduled and unscheduled hemoglobin samples that belong to each window will be taken into account.

